## 4. STUDY POPULATION

### 4.1. Inclusion Criteria

To be eligible for the study, subjects are required to enter the LTS Study within 14 days of exiting the Maintenance Study of Protocol 0157 and must meet all the following criteria:

Capable of providing informed consent, which must be obtained prior to any study-related procedures.

1. One of the following:
  - a. Those who demonstrated persistent [REDACTED] loss of response (no improvement approximately 6 to 8 weeks after meeting loss of response criteria)  
**OR**
  - b. Two Clinical Flares after an episode [REDACTED] of loss of response during the Maintenance Study.  
**OR**
  - c. Those who have completed the Maintenance Study [REDACTED] and have a confirmed clinical remission status (in remission or not in remission) with available results.
2. During the study and for 7 days after receiving the last dose of the study drug, females of childbearing potential or men capable of fathering children must agree to use highly effective birth control measures (failure rate <1% when used consistently and correctly) or agree to abstain from sexual intercourse. Females of childbearing potential must test negative for pregnancy at Day 1. (Refer to Section 4.3).
3. All male subjects must agree to refrain from semen donation during the study and for 7 days after the last dose of study drug.
4. Must be able and willing to adhere to the study visit schedule and comply with other study requirements.

### 4.2. Exclusion Criteria

Subjects meeting any of the following criteria **may not** be enrolled in the study:

#### **Gastrointestinal:**

1. Has current symptoms or signs suggestive of fulminant colitis, toxic megacolon, intestinal perforation
2. Has a high risk of requiring surgery for UC during the study
3. Has been diagnosed during Protocol 0157 with Crohn's disease, microscopic colitis, ischemic colitis, radiation colitis, diverticular disease associated with colitis, indeterminate colitis, or the subject has a current or past diagnosis of a fistula or abdominal abscess

4. Has dysplasia that was not completely resected or high-grade dysplasia detected during Protocol 0157; however, subjects with adenomas with low grade dysplasia that have been completely resected are eligible

**Concomitant or previous medications / treatments:**

5. Taking any medications / treatments listed in [Appendix 4](#) currently or previously during Protocol 0157 Maintenance

**Coexisting medical conditions or past medical history:**

6. Deemed by the investigator to be inappropriate for this study; or has any condition which would confound or interfere with the evaluation of the safety or tolerability of the study drug [e.g., developed unstable or uncontrolled and clinically significant allergic (except for untreated, asymptomatic, seasonal allergies), hematological, endocrine/metabolic, coagulation, immunologic, pulmonary, cardiovascular, hepatic (except hepatic steatohepatitis), GI (except UC), genitourinary, psychiatric, oncologic thrombotic (e.g., deep vein thromboses (DVT) or pulmonary embolism or neurological disease or other medical disorder before during or after Protocol 0157)]; or is unable or unwilling to comply with the study protocol.
7. Develops hypersensitivity to excipients or contents of the study drug as noted in Protocol 0157.
8. Participating in or interested in participating in another investigational study (exception Protocol 0157)
9. Has clinically significant abnormalities in the results of laboratory evaluations at the most recent laboratory evaluation prior to LTS Day 1 visit as determined by the investigator, including:
  - AST, ALT, or alkaline phosphatase  $\geq 2x$  the upper limit of normal (ULN)
  - Total bilirubin  $> 2x$  ULN (unless diagnosis of Gilbert's syndrome)
  - Creatinine clearance as calculated by the Cockcroft-Gault formula  $< 30$  mL/min (Refer to [Appendix 2](#))
  - Total white blood cell count (WBC)  $< 3 \times 10^9/L$
  - Absolute neutrophil count  $< 1.5 \times 10^9/L$
  - Absolute lymphocyte count  $< 0.8 \times 10^9/L$
  - Hemoglobin  $< 8$  g/dL
  - Platelet count  $< 100 \times 10^9/L$ .
10. Subject has had a live viral vaccine (e.g., MMR, varicella zoster, herpes zoster, oral polio virus, FluMist®, attenuated typhoid fever vaccine, attenuated rotavirus vaccine, yellow fever vaccine, or any investigational live vaccine) within 4 weeks prior to Day 1 and/or is unwilling or unable to avoid live viral vaccines during the Study and for 8 weeks following the last dose of study drug. Subject must be willing to avoid contact with any

household member who has been vaccinated with a live attenuated vaccine within 2 weeks after vaccination.

11. Are pregnant, lactating, breastfeeding or planning to become pregnant during the Study or within 7 days after the last dose of Study Drug
12. Within 4 weeks of Day 1, has [1] confirmed severe acute respiratory syndrome coronavirus 2 (SARS-CoV-2) infection (coronavirus disease 2019 [COVID-19]) (test positive), OR [2] suspected SARS-CoV-2 infection (clinical features without documented test results) unless has a negative test for SARS-CoV-2 two weeks after resolution of symptoms and remains asymptomatic until Day 1, OR [3] close contact with a person with known or suspected SARS-CoV-2 infection unless has a negative test for SARS-CoV-2 two weeks after contact and remains asymptomatic until Day 1.

#### **4.3. Women of Childbearing Potential (WOCBP) and Acceptable Birth Controls**

Women of childbearing potential must have documentation of a negative pregnancy test at Day 1 and prior to dosing. All female subjects of childbearing potential must agree to abstain from sexual intercourse or to use a highly effective method of birth control during the study and for at least 7 days after completion of Study drug dosing.

Females are considered not of childbearing potential if they have had a total hysterectomy and/or bilateral tubal ligation or hysteroscopic sterilization (documentation for surgeries must be provided before randomization) or are in a postmenopausal state (i.e., females who have had cessation of prior occurring menses for  $\geq 24$  months without alternative causes or females with premature ovarian failure).

Follicle-stimulating hormone (FSH) will be tested at Day 1 in post-menopausal females only to confirm post-menopausal state.

Highly effective birth control methods are defined as methods that can achieve a failure rate of less than 1% per year when used consistently and correctly. Such methods include: combined (estrogen and progestogen containing) hormonal contraception associated with inhibition of ovulation (oral/intravaginal/transdermal); progestogen-only hormonal contraception associated with inhibition of ovulation (oral/injectable/implantable); intrauterine device; intrauterine hormone-releasing system (IUS); bilateral tubal occlusion; vasectomised partner; sexual abstinence (if this is in line with the preferred and usual lifestyle). Vasectomised partner is a highly effective birth control method provided that partner is the sole sexual partner of the WOCBP trial participant and that the vasectomised partner has received medical assessment of the surgical success. Sexual abstinence is considered a highly effective method only if defined as refraining from heterosexual intercourse during the entire period of risk associated with the study treatments. More restrictive methods of birth control may be required as per local country requirements, and this will be defined in the IRB/IEC approved subject informed consent form.

## **5. STUDY DRUGS**

All Study drug supplied by the Sponsor must be stored in a secure location accessible only to designated study personnel.

### **5.1. Description of Study Drug**

#### **5.1.1. TD-1473**

[REDACTED]

### **5.2. Dosage and Administration**

Subjects will take TD-1473 tablets once daily for up to 156 weeks. Study drug will be self-administered orally. With the exception of the Day 1 visit, Subjects will be instructed to take two tablets once daily at approximately the same time each morning. Subjects will be required to take their first dose in clinic on Day 1. Study drug dispensation will occur at Scheduled Visits as per the Schedule of Study Procedures. Subjects will self-administer their Study drug at home. Subjects will initially utilize the electronic diary to enter Study drug compliance information daily for the first 12 weeks of the LTS Study; subsequently they shall be queried at scheduled visits to recall their UC symptoms and Study drug compliance.

TD-1473 may be taken with or without food. Results from a clinical pharmacology study in healthy subjects showed that there was minimal decrease in plasma exposure of TD-1473 (30% on average) when administered with a high fat meal, relative to fasted conditions. The impact of food on the exposure of TD-1473 is not considered to be clinically meaningful.

### **5.3. Treatment Compliance**

Compliance for the initial 12 weeks will be assessed by subject diary entry. Compliance will also be assessed in subjects when accountability is performed at visits where Study drug is dispensed to or returned by subjects. Treatment compliance will be assessed by reconciliation of used and unused tablets.

Subjects with poor dosing compliance (i.e., < 80% or > 120%), as assessed by tablet counts and/or missing entries on the Study drug administration diary (initial 12 weeks), should receive counseling or assistance, and re-training as appropriate.

#### **5.4. Missed Dose(s)**

The Study drug will be taken orally and must be swallowed whole with liquid and not chewed, divided, dissolved, or crushed. If the subject dose is missed in the morning, it can still be taken up to 12 hours after the subject's nominal dosing time. If the subject does not take the Study drug within 12 hours after the usual time each day, the dose of Study drug should be skipped for that day and the subject should be instructed to take the Study drug on the following day..

#### **5.5. Drug Accountability and Reconciliation**

The investigator or designee is responsible for maintaining accountability records for all Study drug(s) received from the Sponsor, in accordance with applicable government regulations and Study procedures. The accountability record for Study drug (TD-1473) will be maintained in a secure location, accessible only to authorized staff members. The accountability record will include entries for receipt, distribution or dispensing, and destruction of the material(s).

Subjects will be instructed to return all used and unused Study drug at each study visit.

Unused and expired Study drugs will be disposed of in accordance with written instructions from the Sponsor. Drug accountability is maintained in the Randomization and Trial supply management system (RTSM), managed by RTSM supplier.

## **6. STUDY PROCEDURES**

### **6.1. Schedule of Study Procedures**

Study procedures will be performed only after written informed consent is obtained. A subject is considered to be enrolled once the informed consent has been signed.

The Schedule of Study Procedures is summarized in [Table 1](#).

Additional safety tests, such as vital signs (BP, heart rate, respiratory rate, and body temperature), physical exams, ECGs, and laboratory safety tests, may be obtained during the course of the study as clinically indicated to ensure appropriate safety monitoring.

### **6.2. Total Blood Volume**

The total estimated volume of blood to be drawn from each subject for safety laboratory assessments, lipid panel, FSH (If applicable) and [REDACTED] is approximately [REDACTED]. Additional samples may be drawn for safety laboratory testing as considered necessary by the investigator.

### **6.3. Procedures by Visit**

Refer to Section [6.4](#) for detailed description of each of the study assessments.

#### **6.3.1. Day 1**

Subjects meeting all eligibility criteria following exiting the preceding Protocol 0157 Maintenance Study will return to the clinic for enrollment assessments on Day 1.

The Schedule of Study Procedures is summarized in [Table 1](#).

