**Table 1: Schedule of Study Procedures**

Study Procedures	Day 1	WEEK VISITS +/- 5 Days								Early Study Drug Discontinuation l + 5 days from last dose	EOS 4 Weeks Post Last Dose l - 3 to + 5 days
		Year 1	W4	W12		W24	W36	W48	W52		
		Year 2			W60	W72	W84	W96	W104		
		Year 3			W108	W120	W132	W144	W156		
Informed Consent	X										
Review Inclusion/Exclusion Criteria	X										
Physician Global Assessment (PGA)	X		X	X	X	X	X	X	X	X	X
Pregnancy Test (females of child-bearing potential)	X		X e	X e	X e	X e	X e	X e	X e	X e	X e
FSH	X a										
											
In Clinic Dosing - Study Drug Dosing	X k										
Vital Signs (Temp, HR, BP, Respirations)	X l		X l	X l	X l	X l	X l	X l	X l	X	X
Safety Laboratory (Chemistry, Hematology)	X a, m		X	X	X	X	X	X		X	X
Physical Exam	X a		X	X	X	X	X	X	X	X	X
Smoking Status	X a								X		X
Weight	X a								X		
Medical History / Demographics	X a, b										
Concomitant Medication /Adverse Event Review	X		X	X	X	X	X	X	X	X	X
Overnight Fasting Lipid Panel			X	X	X	X	X	X		X	X
											
											
											
12-Lead Electrocardiogram (ECG)	X a			X				X	X		
Study Drug Dispensing	X		X	X	X	X	X	X	X e		
Study Drug Accountability			X	X	X	X	X	X	X	X	
Subject eDiary Daily Compliance Review			X h	X h							
Subject Symptom Recall and Compliance Review					X i	X i	X i	X i	X i	X i	
Dispense Subject eDiary	X h										
Return of Subject eDiary				X h							

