#### **6.3.2. Week 4 and Week 12**

Subjects should be instructed to fast from food and non-clear liquids on the evening prior to the visit to ensure a minimum 8-hour fast prior to the fasted blood sample collection.

The Schedule of Study Procedures is summarized in [Table 1](#).

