**6.4.1.13. Chemistry and Hematology**

Laboratory assessments will be performed as specified in Schedule of Study Procedures (Table 1).

From Day 1 onwards, additional and repeat laboratory safety testing for the evaluation of abnormal results and/or adverse events during the Study may be performed at the discretion of the investigator or upon request of the Sponsor.

Chemistry samples will be analyzed for the following: sodium, potassium, calcium, magnesium, chloride, bicarbonate, glucose, blood urea nitrogen, creatinine, total bilirubin, direct and indirect bilirubin, total protein, albumin, alkaline phosphatase, lactate dehydrogenase, ALT, AST, gamma-glutamyl transferase, and creatine phosphokinase.

Hematology samples will be analyzed for the following: hematocrit and hemoglobin; red blood cell count; mean corpuscular volume; mean corpuscular hemoglobin; mean corpuscular hemoglobin concentration; reticulocyte count; white blood cell count, including differential count (percent and absolute) of neutrophils, eosinophils, basophils, monocytes, lymphocytes; and platelet count.

Detailed instructions and collection kits for sample collection, handling, and shipping will be provided by the central laboratory.

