3.4.3. Additional Safety Assessments

3.4.3.1. Clinical Laboratory Parameters

Laboratory data, hematology, serum chemistry and urinalysis, will be summarized in terms of observed values and changes from baseline. In addition, changes from baseline relative to normal ranges from the central lab (e.g., shifts from normal to abnormal high/low) will be summarized.

The number and percentage of subjects with clinically abnormal lab values will also be summarized by timepoint for the following criteria:

- absolute neutrophil count of $< 1.0 \times 10^9/L$

- white blood cell count of $< 2.0 \times 10^9/L$
- absolute lymphocyte count of $< 0.5 \times 10^9/L$

A listing of all abnormal lab values will be provided.

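### Scheduled follow-up glucose falls at fasting visits, but the plan neither requires nor records a fasted baseline, so glucose change and normal-to-high shifts may be biased downward

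*Protocol*

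**What the plan says.** **Panel.** Protocol 6.4.1.13 puts glucose in the chemistry panel: "Chemistry samples will be analyzed for the following: sodium, potassium, calcium, magnesium, chloride, bicarbonate, glucose", followed by further analytes.

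**Follow-up.** Table 1 of the Protocol schedules chemistry at Weeks 4 and 12, every 12 weeks from Week 24 to Week 144, at Early Study Drug Discontinuation and at End of Study. The row "Overnight Fasting Lipid Panel" has the same post-baseline visits. Section 6.3.2 reads "Subjects should be instructed to fast from food and non-clear liquids on the evening prior to the visit to ensure a minimum 8-hour fast". Sections 6.3.3, 6.3.5 and 6.3.6 give an equivalent instruction.

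**Baseline.** Table 1 schedules chemistry on Day 1 but no lipid panel. Section 6.3.1 says "Subjects meeting all eligibility criteria following exiting the preceding Protocol 0157 Maintenance Study will return to the clinic for enrollment assessments on Day 1", refers to Table 1, and gives no fasting instruction. Section 5.2 allows study drug with or without food, so dosing implies no fast either. Footnote a to the schedule (printed in SAP 1.4) lets a procedure done in Protocol 0157 in the preceding 14 days replace the Day 1 procedure. Footnote m treats a Day 1 laboratory draw as conditional.

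**Analysis.** SAP 3.1.1 takes the last scheduled pre-dose value as baseline, and SAP 5.2.2.4 replaces a missing laboratory baseline with the last available assessment. Neither sets a fasting condition. Under SAP 3.4.3.1 laboratory data, "hematology, serum chemistry and urinalysis, will be summarized in terms of observed values and changes from baseline", with shifts against the normal range in addition.

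**The concern.** A change from baseline is interpretable when both values are taken under comparable conditions. Here one side is controlled and the other is not. If some baseline samples were drawn after food, and food raises glucose, those baselines are too high relative to fasting follow-up. Mean change then moves down, and some subjects who would have counted as normal at baseline are classed as high and cannot contribute a normal-to-high shift.

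Change in laboratory tests is part of the primary safety endpoint. The study has no placebo arm (SAP 1.2), so no untreated group would show the same artefact. The SAP's counts of abnormal laboratory values cover only neutrophils, white cells and lymphocytes, so the change and shift tables carry much of the summarised information on glucose.

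**Working it through.** The plan states no figure on this point, so there is none to reproduce.

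**1. Schedule check.** Scheduled post-baseline chemistry: Weeks 4, 12, 24, 36, 48, 60, 72, 84, 96, 108, 120, 132 and 144 (13 visits), plus Early Discontinuation and End of Study, giving 13 + 2 = 15. Visits with a fasting instruction in 6.3.2, 6.3.3, 6.3.5 and 6.3.6: the same 15. Weeks 52, 104 and 156 have neither chemistry nor a fasting instruction. Day 1 has chemistry and no fasting instruction.

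**2. Bias in mean change.** Let p be the share of baselines drawn unfasted and d the mean fed-minus-fasted difference in glucose. With fasted follow-up,

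expected observed change = true change − p × d.

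The documents give neither p nor d, so both are varied. For an assumed true rise of 5 mg/dL, the observed mean change (mg/dL) is:

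| p | d = 10 | d = 20 | d = 30 |
|---|---|---|---|
| 0 | 5.0 | 5.0 | 5.0 |
| 0.10 | 4.0 | 3.0 | 2.0 |
| 0.25 | 2.5 | 0.0 | −2.5 |
| 0.50 | 0.0 | −5.0 | −10.0 |

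For example, 5 − 0.25 × 20 = 0, and 5 − 0.50 × 20 = −5.

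**3. Normal-to-high shifts.** These were simulated with assumed values: fasting mean 95 mg/dL, between-subject SD 10, within-subject SD 6, upper limit 110, true rise 5, and a fed increment with mean d and SD 15. The SAP does not state the denominator, so both are shown.

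| Setting | % of all subjects | % of subjects with normal baseline |
|---|---|---|
| all baselines fasted | 12.4 | 13.8 |
| p = 0.50, d = 10 | 9.5 | 12.7 |
| p = 0.50, d = 20 | 7.8 | 12.0 |
| p = 0.50, d = 30 | 6.8 | 12.2 |

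Most of the fall in the first column arises because fewer subjects are classed as normal at baseline. Among those who are, the loss is 1.1 to 1.8 percentage points.

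**4. Sensitivity to the assumptions.** With fasting mean 92, SDs 8 and 5, upper limit 99 and a constant fed increment of 10, the all-subject rate falls from 22.6% to 13.5% at p = 0.50. The rate among subjects with a normal baseline falls from 29.3% to 23.5%. The direction is the same, but the size depends on inputs the documents do not supply.

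**The case against.** The strongest reply is that no mismatch has been shown. Entry must fall within 14 days of leaving Protocol 0157, the same length as the carry-over window, so a 0157 sample may well be the baseline for many subjects. Its fasting rules are in a protocol not provided here. The central laboratory's collection instructions, mentioned in Protocol 6.4.1.13, are not available either. This stands: the baseline fasting state is uncontrolled in these documents, not known to be unfasted.

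A reader might infer that every follow-up sample is fasted, every baseline is fed, and the tables therefore hide a rise in glucose. The documents do not support that. The fasting text is tied to the fasted blood sample, which is the lipid panel, so fasted chemistry is inferred from the shared visit. Repeat tests have no fasting rule, and the latest-record rule in SAP 3.1.4 can bring one into a visit summary.

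The consequences are also limited. No inferential tests are planned. Observed values are summarised and abnormal values listed, so a high fasting glucose during treatment stays visible. Glucose is not among the laboratory abnormalities of concern in Protocol 7.2. Subjects who continue an active Maintenance dose have a baseline already on drug, so an earlier drug effect would not appear as change even with perfect fasting. These points limit the importance of the problem. They do not make the change table reliable, because nothing in the protocol or SAP would show whether it is affected.

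**Conclusion.** The asymmetry is confirmed: 15 of 15 scheduled post-baseline chemistry visits have a fasting instruction, and the baseline has neither a fasting requirement nor a record of fasting status. Glucose change from baseline may be biased downward by p × d. That is 5 mg/dL at 25% unfasted and +20 mg/dL, enough to cancel a true rise of 5, and zero if all baselines were fasted. The effect on shifts is small in the main illustration when they are counted among subjects with a normal baseline, and varies with the assumed distribution and upper limit.

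The direction rests on unfasted glucose being higher than fasted; the size rests on assumed p and d. The supported conclusion is a possible, unmeasured bias in two derived displays of one analyte. It is not that a rise in glucose has been hidden.

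**What to change.** **Protocol 6.3.1.** Add the fasting instruction of 6.3.2 for subjects whose chemistry sample is drawn on Day 1. Record fasting status with the baseline chemistry sample, including one carried over from Protocol 0157. The SAP's Introduction says that the last doses were given by 09SEP2021 and the last visits held by 11OCT2021, so this part can help only a later protocol built on the same schedule.

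**SAP 3.4.3.1.** Recover baseline fasting status where source data allow, and restrict or stratify the glucose change and shift summaries by it. Where status cannot be recovered, make observed glucose at the fasting visits the main summary, and footnote the change and shift tables to say that baseline fasting status is unknown.

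**Cost.** One sentence in 6.3.1, one CRF field, one SAP sentence and a footnote. Subjects would face an overnight fast before Day 1, and fewer of them would enter the glucose change table. No sample-size figure changes.
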